6.2. Secondary Endpoint(s)

6.2.1. Overall Survival

Estimand strategy: treatment policy.

Analysis set: Safety analysis set.

Analysis methodology: using Kaplan-Meier method, plot the estimation of the survival function and estimate its associated statistics on OS (including the quartiles of OS with two-sided 95% CI, the OS rates at clinical meaningful timepoints with two-sided 95% CI). The CI for the quartiles will be calculated according to Brookmeyer and Crowley method, and the CIs for the survival probability estimates at the timepoints will be derived using the log(-log) method.

Intercurrent events: the analysis is conducted without regard to discontinuation from treatment or start of new anti-cancer therapy.

Participants without confirmation of death will be censored on date of last contact.

Frequency (number and percentage) of participants with an event (death) and censoring reasons will be presented. Censoring reasons are as follows: alive, withdrawal of consent and lost to follow-up.

6.2.2. Progression-Free Survival

6.2.2.1. Main Analysis

Progression-Free Survival (PFS) is defined as the time from date of first dose to the date of the first documentation of disease progression (ie, objective progression, relapse from CR/CRi) as assessed by the investigator, or death due to any cause, whichever occurs first.

Estimand strategy: Hypothetical strategy. The analysis will consider intercurrent events of start of subsequent new induction therapy and an extended gap in tumor assessment prior to an assessment of disease progression or death.

Analysis set: Safety analysis set.

Intercurrent events and missing data: Partial dates will be imputed as described in [Section 5.3](#). No other imputations for missing data will be performed. PFS data will be censored as follows:

- For participants who start a new induction therapy (as defined in [Section 5.2.5](#)) prior to an event, censoring will be at the last adequate tumor assessment prior to the start of new induction therapy. Note: if date of progression occurs on the same date as the start of new induction therapy, the progression will be counted as an event.
- For participants who do not have an adequate baseline tumor assessment or any post-baseline tumor assessments, censoring will occur on the date of first dose unless death occurred on or before 12 weeks after first dose in which case the death will be considered an event.
- For participants having adequate baseline tumor assessment and without defined PFS events, censoring will occur on the date of last valid disease assessment (date of first dose if no post-baseline assessment).
- For participants with defined PFS events occurring after an unacceptable long interval (>28 weeks if there was post-baseline disease assessment, or >12 weeks if there was no post-baseline assessment) since the previous disease assessment, censoring will occur at the date of the previous assessment (or date of first dose if there is no post-baseline assessment).

Analysis methodology: The Kaplan-Meier method will be used to plot the estimated survival function and estimate its associated statistics on PFS (including the median PFS with two-sided 95% CI, the PFS rates at clinical meaningful timepoints with two-sided 95% CI) for safety analysis set without regard to discontinuation from treatment.

Frequency (number and percentage) of participants with each event type (disease progression or death) and censoring reasons will be presented along with the overall event and censor rates.

Reasons for censoring should be summarized according to the categories in Table 2. If a participant meets multiple definitions for censoring the list will be used to define the hierarchy.

Table 2. Censoring Reasons and Hierarchy

Hierarchy	Condition	Censoring Reason
1	No adequate baseline assessment.	No adequate baseline assessment
2	Start of new induction therapy before event.	Start of new induction therapy
3	Event more than 28 weeks if there was post-baseline disease assessment, or more than 12 weeks if there was no post-baseline assessment after previous tumor assessment.	Event after missing assessments ^a
4	No event and [withdrawal of consent date \geq start date OR End of study (EOS) = WITHDRAWAL BY SUBJECT.	Withdrawal by participant
5	No event and lost to follow-up in any disposition page.	Lost to follow-up
6	No event and EOS present and no adequate post-baseline tumor assessment.	No adequate post-baseline tumor assessment
7	No event and none of the conditions in the prior hierarchy are met.	Ongoing without an event

^a more than 28 weeks if there was post-baseline disease assessment, or more than 12 weeks if there was no post-baseline assessment after previous tumor assessment.

The PFS time or censoring time and the reasons for censoring will also be presented in a data listing.

6.2.2.2. Sensitivity Analysis

Sensitivity analysis for PFS is conducted in the same fashion as in [Section 6.2.2.1](#) except that the PFS event is now expanding to include treatment discontinuation due to global deterioration of health status and starting new induction therapy/post-therapy HSCT without achieving CR/CRI.

Specifically, PFS in this section is defined as the time from date of first dose to the date of disease progression (ie, objective progression, relapse from CR/CRI, treatment discontinuation due to global deterioration of health status), death due to any cause, or starting new induction therapy/post-therapy HSCT without achieving CR/CRI, whichever occurs first (including post-study treatment follow-up disease assessments).

As a consequence, for participants who do not achieve CR/CRI, starting of new induction therapy is no longer an intercurrent event for estimand purpose, and the start of new induction therapy in hierarchy #2 of Table 2 should be ignored for censoring reasoning among that group of participants.

All other censoring rules, analysis methodology and summaries (including censoring reason) from [Section 6.2.2.1](#) still apply in this section.

6.2.3. Duration of Remission

Duration of remission (DoR) is defined as the time from date of first response in responders (CR/CRI) to the date of disease progression (ie, objective progression, relapse from CR/CRI), death due to any cause, whichever occurs first (including post-study treatment follow-up).

The censoring rules for DoR are as described for PFS in Section 6.2.2.1, but the censoring occurs on the date of first dose for PFS analysis will occur on the date of first remission of responders for DOR analysis.

The Kaplan-Meier method will be used to plot the estimated survival function and estimate its associated statistics on DoR (including the median DoR with two-sided 95% CI) for responders to investigational product without regard to discontinuation from treatment.

This analysis is based on responders in the safety analysis set.

The CI for the median DoR will be calculated according to Brookmeyer and Crowley method.

Duration of Complete Remission (DoCR) and Duration of Complete Remission with Incomplete Hematologic Response (DoCRI) will also be analyzed separately in the safety analysis set following the same methods described above. DoCR is defined as the time from the date of CR in participants who achieved a CR to the date of disease progression (ie, objective progression, relapse from CR/CRI) as assessed by the investigator, or death due to any cause, whichever occurs first. DoCRI is defined as the time from the date when a CRI is first achieved to the date of disease progression (ie, objective progression, relapse from CR/CRI) as assessed by the investigator, or death due to any cause, whichever occurs first. The censorship of DoCR and DoCRI follows the same as DoR.

Note that DoCRI is the same as DoR for CRI participants.

6.2.4. MRD Negativity

Minimal residual disease (MRD) negativity is defined as in Section 3.2.1. Number and percentage of participants with MRD negativity among participants who achieve CR/CRI will be reported. The count and percentage will be summarized descriptively as well as the corresponding two-sided 95% CI using Clopper-Pearson exact method.

The analysis is based on responders in the safety analysis set.

6.2.5. HSCT

HSCT prior and post inotuzumab ozogamicin will be summarized by descriptive analyses (ie, the count, percent of participants proceeding to HSCT and the associated 2-sided 95% CI using Clopper-Pearson exact method. This analysis is based on safety analysis set.

If there are considerate number of participants who undergo HSCT post Inotuzumab ozogamicin, post transplant mortality, post transplant relapse and non-relapse mortality may be analyzed accordingly.

6.2.6. Pharmacokinetic/Pharmacodynamics

Pharmacokinetic concentration analyses will be based on the PK concentration analysis set.

Descriptive summary statistics will be provided for serum concentration at scheduled visits. Serum concentration value below the limit of quantitation will be treated as zero in the descriptive statistics calculation. N, mean, standard deviation, percent coefficient of variation (%CV), median, range, geometric mean and geometric %CV will be presented by cycle, day and nominal time in tabular form.

PK and PD data from this study may be analyzed using compartmental modeling approaches and may also be pooled with data from other studies to investigate any association between inotuzumab ozogamicin exposure and biomarkers or significant safety and/or efficacy endpoints. The results of these modeling analyses, if performed, will be reported separately from the clinical study report.

6.3. Other Endpoint(s)

6.3.1. Incidence of anti-drug antibody (ADA) and neutralizing antibody (NAb)

The percentage of participants with positive ADA and NAb will be summarized using immunogenicity population. The magnitude (titer), time of onset, duration of ADA and NAb will also be described if data permits.

6.4. Subset Analyses

Estimate the CR/CRI rate per investigator's assessment for participants who receive at least one dose of investigational product from the time of first dose until the end of treatment for each of the participants stratum characterized by baseline CD22 $\geq 90\%$, $90\% > CD22 \geq 70\%$, and $CD22 < 70\%$

6.5. Baseline and Other Summaries and Analyses

6.5.1. Baseline Summaries

Analyses of baseline data will be based on the safety analysis set.

6.5.1.1. Demographic Characteristics

The following demographic and baseline characteristics will be summarized by number and percentage:

- Gender (male, female).
- Age (18- <45 ; 45- <65 ; ≥ 65).
- Eastern Cooperative Oncology Group (ECOG) Performance status.

will be summarized by category (number and percent).

Age (continuous), height (cm), weight (kg), Body Mass Index (BMI) (kg/m²), Body Surface Area (BSA) (m²) will be summarized with descriptive statistics (mean, median, standard deviation, Q1, Q3, minimum, and maximum).

6.5.1.2. Medical History

Medical history will be coded using the most current version of MedDRA and summarized by MedDRA's System Organ Class (SOC) and PT from the 'Medical History' eCRF page. Each participant will be counted only once within each PT or SOC. Summaries will be ordered by primary SOC and PT in descending order of frequency by the experimental treatment arm. Separate summaries will be provided for past and present conditions.

6.5.1.3. Disease Characteristics

The following baseline disease characteristics will be summarized by number and percentage:

- Primary diagnosis (if all participants have the same diagnosis this may be omitted).
 - Time since initial diagnosis (months), defined as (date of first dose – date of initial diagnosis)/30.4375, will be summarized by descriptive statistics (mean, median, standard deviation, minimum, and maximum).
 - Cytogenetics (Abnormal, Normal, Unknown) and cytogenetics abnormality details

6.5.1.4. Prior Anti-cancer Therapy

The prior anti-cancer therapies are collected under the 'Prior Cancer Therapy', 'Prior Radiation Therapy' and 'Prior Surgery' eCRF pages.

The number and percentage of participants in each of the following anti-cancer therapy categories will be tabulated:

- Participants with at least one type of prior anti-cancer treatment;
- Participants with at least one prior anti-cancer drug therapy;
- Participants with at least one prior anti-cancer radiotherapy;
- Participants with at least one prior anti-cancer surgery
- Participants with at least one prior HSCT
 - Participants in salvage 1 and 2;Salvage 1: Morphological relapse after initial treatment or resistant disease (no CR/CRi) after initial treatment;

- Salvage 2: Morphological relapse after salvage 1 therapy or resistant disease after salvage 1.

Prior anti-cancer drug therapy will be summarized as follows based on the number and percentage of participants:

- Number of prior anti-cancer therapy regimens: missing/1/2/3/ ≥ 4 ;
- Intent of Therapy: induction, consolidation, maintenance, conditioning or intensification.

The prior anti-cancer drugs will be coded in the WHO Drug coding dictionary and will be summarized based on the number and percentage of participants by preferred term. A participant will be counted only once within a given preferred term, even if he/she received the same medication at different times. The summary will be sorted on decreasing frequency. In case of equal frequency, alphabetical order will be used.

Specific details on surgeries and radiotherapy will be listed.

6.5.2. Study Conduct and Participant Disposition

6.5.2.1. Disposition

The percentages below will be calculated based on the number of enrolled participants .

- Number of participants who discontinued from the study prior to first dose overall and by the main reason for discontinuation.
- Number and percentage of participants in each of the analysis sets defined in [Section 4](#).
- Number and percentage of participants with study drug ongoing, discontinued or not given.
- Number and percentage of participants who discontinued study drug overall and by the main reason for discontinuation of study drug.
- Number and percentage of participants who entered follow-up.
- Number and percentage of participants who discontinued follow-up overall and by the main reason for discontinuation.

6.5.2.2. Protocol Deviations

Protocol deviations will be compiled prior to database closure and will be summarized by category (n(%)) for the safety analysis set for treatment arm. Categories will be assigned by the study Clinician.

6.5.3. Study Treatment Exposure

Exposure will be summarized for the safety analysis set.

6.5.3.1. Exposure to Inotuzumab Ozogamicin

The summary of treatment exposure for inotuzumab ozogamicin will include the following information (by dose level for safety population):

- Treatment duration (weeks).
- Treatment cycles.
- Cumulative dose (mg/m^2).
- Dose intensity (DI, $\text{mg}/\text{m}^2/\text{cycle}$).
- Relative dose intensity (RDI, %).

The duration of inotuzumab ozogamicin (in weeks) is defined as:

$$\text{Treatment duration (weeks)} = (\text{last dose date} - \text{first dose date} + 1)/7.$$

The cumulative dose (mg/m^2), the dose intensity (DI) and the relative dose intensity (RDI) of inotuzumab ozogamicin in each cycle and overall will be calculated for each participant.

The cumulative dose (mg/m^2) of inotuzumab ozogamicin in a cycle or overall will be the sum of the actual dose levels that the participant received (ie, total dose administered [mg/m^2]).

The dose intensity (DI, $\text{mg}/\text{m}^2/\text{cycle}$) of inotuzumab ozogamicin during the study will be defined as follows:

- Overall DI ($\text{mg}/\text{m}^2/\text{cycle}$) = [overall cumulative dose (mg/m^2)]/[number of cycles].

The RDI of inotuzumab ozogamicin will be defined as the ratio of the DI and planned dose intensity and expressed in percentage as follows:

- By cycle RDI (%) = $100 \times [\text{cumulative dose in the cycle}]/[\text{planned cumulative dose per cycle}]$;
- Overall RDI (%) = $100 \times [\text{overall cumulative dose}]/[\text{overall planned cumulative dose}]$.
- Overall planned cumulative dose is the sum of planned doses across all cycles that the participant planned before receiving the actual doses.

6.5.3.2. Dose Reductions and Delays

A dose reduction is defined as a non-zero dose that is less than the planned dose.

The number and percentage of participants with at least one dose reduction as well as a breakdown of dose reductions (1/2/3/ ≥ 4) will be summarized for safety population.

A dose delay is defined for non-continual dosing regimens, in this case inotuzumab ozogamicin, and will be derived based on study drug administration date and will be grouped into the following categories based on the deviation of the actual to the planned treatment administration day (relative to the previous treatment administration date):

- No delay (including 1-2 day delays).
- 3-6 days delay.
- 7 or more days delay.

For example, for inotuzumab ozogamicin, administered on a 1-week schedule, if one participant receives inotuzumab ozogamicin on Day 1, then the next inotuzumab ozogamicin administration date will be on Day 8; however, if the participant receives inotuzumab ozogamicin at Day 9 or 10, this is not considered as a delay.

The number and percentage of participants with delayed study drug administration and maximum length of delay, ie, the worst case of delay if participants have multiple dose delays will be summarized, as applicable.

Reasons for delays will be summarized. Participants can contribute to more than one reason if multiple dose delays occurred for different reasons, but will only be counted once per reason. Percentages will be calculated based on the total number of participants in safety analysis set.

6.5.4. Concomitant Medications and Nondrug Treatments

The following analyses will be based on the safety analysis set for treatment arm.

Concomitant medications are medications, other than study medications, which started prior to first dose date of study treatment and continued on on-treatment period as well as those started during the on-treatment period. **Prior medications** are medications, other than study medications and pre-medications for study drug, which are started before the first dose of study treatment.

Summary of prior medications, summary of concomitant medications and summary of pre-medications will include the number and percentage of participants by Anatomical Therapeutic Chemical (ATC) Classification level 2 and preferred term. A participant will be counted only once within a given drug class and within a given drug name, even if he/she received the same medication at different times. If any prior or concomitant medication is classified into multiple ATC classes, the medication will be summarized separately under

each of these ATC classes. The summary tables will be sorted on decreasing frequency of drug class and decreasing frequency of drug name in a given drug class. In case of equal frequency regarding drug class (respectively drug name), alphabetical order will be used. In case any specific medication does not have ATC classification level 2 coded term, it will be summarized under 'Unavailable ATC classification' category.

A listing of prior medications and a listing of concomitant medications will be created with the relevant information collected on the 'General Concomitant Medications' eCRF page. A listing of pre-medications will be created with the relevant information collected on the 'Pre-Medication Treatment' eCRF page.

All concurrent procedures, which were undertaken any time during the on-treatment period, will be listed according to the eCRF page 'General Non-drug Treatments'.

A listing of concurrent procedures will be created with the relevant information collected on the 'General Non-drug Treatments' eCRF page.

6.5.5. Subsequent Anti-cancer Therapies

The following analyses will be based on the safety analysis set.

Anti-cancer treatment will be provided in a data listing with data retrieved from related eCRF pages.

Number and percentage of participants with any anti-cancer therapy after discontinuation will be tabulated overall and by type of therapy based on the data collected from the 'Follow-up Cancer Therapy', 'Follow-up Radiation Therapy' and 'Follow-up Surgery' eCRF pages.

6.6. Safety Summaries and Analyses

Summaries of AEs and other safety parameters will be based on the safety analysis set.

6.6.1. Adverse Events

All analyses will be based on treatment emergent events unless otherwise specified. Treatment emergent is defined in [Section 3.5.1](#). AEs not considered treatment emergent will be flagged in data listings.

A high level summary of TEAEs (all causality), TEAEs (treatment related) and Cycle 1 TEAEs (treatment related) will include the number and percentage of participants with:

- Any TEAE;
- Serious TEAE;
- TEAE with CTCAE Grade 3-4;
- Grade 5 TEAE;

- TEAEs leading to dose reductions of inotuzumab ozogamicin;
- TEAEs leading to dose delay of inotuzumab ozogamicin;
- TEAEs leading to permanent discontinuation of inotuzumab ozogamicin.

Additionally, the number of events reported for each of the categories above will be provided. Each unique adverse event at the PT level for a participant is included in the count.

Seriousness, toxicity grade, action taken (interruption, reduction, and withdraw) are as reported by the investigator on the adverse event CRF.

Summaries of TEAE by SOC and PT in decreasing frequency will be provided for:

- TEAEs (All Causality);
- TEAEs by Maximum Toxicity Grade (All Causality);
- TEAEs (Treatment related);
- TEAEs by maximum toxicity grade (Treatment related);
- Serious TEAEs (All causality);
- Post-HSCT SAE (All causality);
- Serious TEAEs (Treatment related); and
- Post-HSCT SAE (Treatment related).

An event will be considered treatment related if the investigator considers so.

The following summaries will be provided by PT only (ie, summaries will not include SOC) in decreasing frequency:

- TEAEs (All causality);
- TEAEs (All causality) experienced by $\geq 10\%$ of participants;
- TEAEs (All causality) by maximum toxicity grade;
- Grade 3-5 TEAEs (All causality and Treatment related);
- TEAEs leading to dose delays of inotuzumab ozogamicin (all causality);
- TEAEs leading to dose reductions of inotuzumab ozogamicin (all causality);

- TEAEs leading to permanent discontinuation of inotuzumab ozogamicin (all causality);
- Serious TEAEs (all causality); and
- Post-HSCT SAEs (all causality).

Each participant will be counted only once within each SOC and PT.

As described in [Section 5.3](#), in case a participant has events with missing and/or non missing toxicity grades, the maximum of the non-missing grade will be displayed. Missing grade will only be displayed in the event that only one event has been reported for a participant and the grade is missing.

6.6.1.1. Adverse Events of Special Interest

All cases of VOD/SOS irrespective of causality or severity will be reported as SAEs for up to 2 years after the first dose of inotuzumab ozogamicin.

If data permits, number and percentage in patients with VOD/SOS and in patients with VOD/SOS following post-study HSCT will be summarized. The VOD/SOS patients above are also summarized considering different risk factors, including prior study HSCT (yes/no), prior history of hepatic disease (yes/no), baseline ALT/AST/Total serum bilirubin abnormal by CTCAE (Grade 0,1).

Summary of AESI by PT will also be provided.

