### 3. OBJECTIVES, ESTIMANDS, AND ENDPOINTS

Objectives	Estimands	Endpoints
Primary:		

To evaluate the efficacy of inotuzumab ozogamicin based on a primary endpoint of complete remission [CR]/complete remission with incomplete hematologic recovery [CRi] per Investigator's assessment in Chinese adult patients with relapsed/refractory B-cell ALL.

	

The treatment effect of inotuzumab ozogamicin from the time of first dose until end of treatment for all patients who received at least one dose of inotuzumab ozogamicin regardless of tolerability and duration on treatment.

	

CR/CRi per investigator's assessment.

Objectives	Estimands	Endpoints
Secondary:		

To evaluate the efficacy of inotuzumab ozogamicin.

To evaluate the safety of inotuzumab ozogamicin.

To evaluate PK of inotuzumab ozogamicin

To evaluate the immunogenicity of inotuzumab ozogamicin

		

Duration of remission (DoR).

Minimal residual disease (MRD) negativity in patients achieving CR/CRi.

Progression-free survival (PFS).

Overall survival (OS).

Hematopoietic stem cell transplant (HSCT).

AEs and laboratory abnormalities by type, frequency, severity (as graded by NCI CTCAE v5.0), timing, seriousness, and relationship to study therapy, including VOD (total, during study treatment, and post-HSCT).

Inotuzumab ozogamicin <math>C_{max}</math> and <math>C_{trough}</math>.

Incidence of anti-drug antibodies (ADA) and neutralizing antibodies (NAb).

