#### 9.4.2. Safety Analyses

The safety analysis will be conducted on the safety population. AEs will be presented with and without regard to causality based on the Investigator's judgment. The frequency of overall toxicity, categorized by toxicity Grades 1 through 5, will be described. Additional summaries will be provided for AEs that are observed with higher frequency.

Rate of VOD/SOS (total, on-study treatment, and post-HSCT) will be summarized in the safety population. Descriptive analyses (ie, the number, percent of patients with VOD along with 2-sided 95% CI) will be presented. A subgroup analysis will also be conducted for VOD in patients who undergo HSCT in the safety population. Analyses in this subgroup will include an assessment of VOD in all patients with a subsequent HSCT as well as in patients who proceed to HSCT directly after inotuzumab ozogamicin treatment (without an intervening induction therapy). All known cases of VOD, regardless of causality and severity, will be reported as SAEs for the entire duration of study participation, including the Follow-up period.

Drug exposure will be summarized using descriptive statistics.

Laboratory data will be summarized by the type of laboratory test. Summary of Laboratory abnormalities will be presented by maximum CTCAE Grade. A shift summary of baseline grade by maximum post-baseline grade will also be presented. Parameters which cannot be graded will be summarized relative to the normal range (ie, higher or lower than normal range). Vital signs data will be summarized using descriptive statistics (mean, standard deviation, median, quartiles, minimum, and maximum) of actual values and change from baseline for each nominal visit over time (ie, unscheduled assessments will be excluded).

The number and percentage of patients with abnormal findings in physical examination will be summarized by body system for each nominal assessment timepoint.

Exploratory analysis may be performed to assess relationship between CD22 and efficacy (including MRD) and/or safety outcomes if data permit, the details will be decrypted in the SAP.

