3.5. Safety Endpoints

Safety endpoints will be summarized based on the on-treatment period unless otherwise specified.

On-treatment is defined as the time from the first dose of study treatment through minimum (9 weeks after the last administration of the investigational product, start day of new anti-cancer therapy – 1 day). The start date of new anti-cancer therapy after the first dose of study treatment is derived as outlined in [Section 5.2.5](#). Adverse events occurring on the same day as the first dose of study treatment will be considered to have occurred during the on-treatment period. All other assessments which occur on the same day as the first dose of study treatment will be considered baseline assessments (see [Section 3.4](#) for the definition of baseline). If the exact time is collected, the last assessment before the time of first dose of study treatment will be considered as baseline assessments.

Safety data collected outside the on-treatment period as described above will be listed but not summarized.

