3.5.1. Adverse Events

Adverse events (AEs) will be coded to preferred term (PT) and system organ class (SOC) using the Medical Dictionary for Regulatory Activities (MedDRA) and classified by severity using the National Cancer Institutes (NCI) Common Terminology Criteria for Adverse Events (CTCAE), version 5.0. For other AEs without specific NCI CTCAE v5.0 definitions, results will be identified according to NCI CTCAE v5.0 “other” categories.

An event will be considered treatment related if the investigator considers so.

An adverse event is considered treatment-emergent relative to a given treatment if the event start date is during the on-treatment period (including on the date of first dose). All cases of VOD/SOS irrespective of causality or severity will be reported as SAEs for up to 2 years after the first dose of inotuzumab ozogamicin.

Adverse Events of Special Interest (AESI)

AEs of special interest (AESI) are as follows:

- GRADE ≥ 3 HEPATOTOXICITY AND/OR SERIOUS HEPATOTOXICITY, INCLUDING VOD/SOS;
- MYELOSUPPRESSION/CYTOPENIA;
- INTERSTITIAL LUNG DISEASE;
- INFLAMMATORY GASTROINTESTINAL EVENT;
- PANCREATITIS;
- SECONDARY PRIMARY MALIGNANCY;

- REPRODUCTIVE AND DEVELOPMENT TOXICITY;
- NEPHROTOXICITY; and
- NEUROTOXICITY.

These events are defined in [Appendix 2](#).

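### SAP 6.6.1.1 leaves out the 95% CIs, the direct-to-HSCT rate and the labelled on-treatment rate that protocol 9.4.2 promises for VOD, and the counting window for VOD is not stated

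*SAP*

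**What the plan says.** **Protocol.** Section 3 makes VOD part of a secondary endpoint in three forms: "relationship to study therapy, including VOD (total, during study treatment, and post-HSCT". Section 9.4.2 carries this into the analysis: "Rate of VOD/SOS (total, on-study treatment, and post-HSCT) will be summarized in the safety population". It then gives the statistics: "Descriptive analyses (ie, the number, percent of patients with VOD along with 2-sided 95% CI) will be presented". It adds a subgroup analysis covering everyone with a subsequent HSCT and also "patients who proceed to HSCT directly after inotuzumab ozogamicin treatment (without an intervening induction therapy". None of this is conditional. Section 8.4.1 collects VOD through long-term follow-up whether or not new anti-cancer treatment has begun.

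**SAP.** Section 6.6.1.1 says: "If data permits, number and percentage in patients with VOD/SOS and in patients with VOD/SOS following post-study HSCT will be summarized". It adds breakdowns by risk factor and an AESI summary by preferred term. Section 3.5 sets the general rule: "Safety endpoints will be summarized based on the on-treatment period unless otherwise specified". The window ends at the earlier of 9 weeks after the last dose and the day before new anti-cancer therapy. Beyond it: "Safety data collected outside the on-treatment period as described above will be listed but not summarized". Section 6.6.1 sets a matching treatment-emergent default, also with room for exceptions. Sections 3.2.2, 3.5.1 and 6.6.1.1 each state that "All cases of VOD/SOS irrespective of causality or severity will be reported as SAEs for up to 2 years after the first dose" of study drug.

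**The concern.** VOD is the hepatic risk that the protocol dwells on most. It has its own adjudication committee, a 2-year reporting rule and a place in a secondary endpoint. A SAP is where such a commitment becomes table shells. Here the shells as described would not produce the CIs, the direct-to-HSCT rate or a row identified as on-treatment VOD.

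The second problem is what the overall count contains. The 2-year sentence speaks of reporting VOD as SAEs and does not say which events enter the summary. Two programmers could reach different overall counts from the same data, and the AESI table could disagree with the dedicated VOD summary without explanation. Most VOD in the pivotal study followed transplant, so the choice of window can matter a good deal.

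**Working it through.** **Promised rows against planned rows**

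- *Total VOD.* Protocol 9.4.2: n, % and 95% CI. SAP 6.6.1.1: n and %, if data permit, window not stated.
- *On-treatment VOD.* Protocol: n, % and CI. SAP 6.6.1.1: no labelled row. Treatment-emergent counts can be read from the TEAE and AESI tables by preferred term (6.6.1, Appendix 2), without CI.
- *Post-HSCT, all transplanted.* Protocol: n, % and CI. SAP 6.6.1.1: n and %, if data permit. The post-HSCT SAE tables in 6.6.1 are unconditional, with no CI and no stated HSCT denominator.
- *Post-HSCT, direct.* Protocol: promised. SAP: absent.

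No other SAP section fills the gaps. Section 5.2.12 limits qualitative variables to counts and percentages by default. Sections 6.2.4 and 6.2.5 do specify Clopper-Pearson CIs for MRD negativity and HSCT, so the method is already in the plan.

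**Pivotal figures (protocol 2.2.2.1.1 and 2.2.2.1.3.1), reproduced**

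- Total 23/164 = 14.0%; without HSCT 5/164 = 3.0%; post-HSCT 18/79 = 22.8%.
- Share of VOD that followed HSCT: 18/23 = 78%.
- HSCT rate 79/164 = 48.2%; direct 71/79 = 89.9%.

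**Illustration for 44 patients, assuming those rates carry over**

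- Transplanted: 44 × 79/164 = 21.2. Direct: 44 × 71/164 = 19.0.
- VOD without HSCT: 44 × 5/164 = 1.34. VOD after HSCT: 44 × 18/164 = 4.83. Total: 6.17.
- If the HSCT rate were 30% or 70%, the non-HSCT figure held at 1.34: 44 × 0.30 × 18/79 + 1.34 = 4.35, and 44 × 0.70 × 18/79 + 1.34 = 8.36.

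**Overall count under three readings (Clopper-Pearson 95% CI)**

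1. No window: about 6/44 = 13.6% (5.2–27.4%).
2. Windowed, and conditioning counts as new anti-cancer therapy: post-HSCT cases drop out, leaving about 1/44 = 2.3% (0.1–12.0%). The pivotal cases without HSCT arose by 56/7 = 8.0 weeks after the last dose, inside 9 weeks, so such a table would approximate the on-treatment rate, unlabelled.
3. Windowed, and conditioning does not count: some post-HSCT cases stay in. The pivotal medians, 4.9 weeks from last dose to HSCT and 15 days from HSCT to VOD, add to 4.9 + 15/7 = 7.0 weeks. The range ends add to 1 + 3/7 = 1.4 and 19 + 57/7 = 27.1 weeks.

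For reading 3, I simulated the two intervals as independent log-normals with these medians and assumed log-SDs of 0.5–0.75 (gap to HSCT) and 0.7–0.9 (onset of VOD). Between 57.7% and 66.2% of direct-transplant cases fall inside 9 weeks. The 4.9-week gap describes only the 71 direct transplants. The other 8 of 79 are taken to have had intervening induction, which closes the window, and average VOD risk. The share of all post-HSCT cases is then 71/79 × (57.7 to 66.2%), or about 52–60%. The count is 1.34 + 4.83 × (0.52 to 0.60) = 3.9 to 4.2, about 4/44 = 9.1% (2.5–21.7%).

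**What a missing CI hides.** 5/21 = 23.8% (8.2–47.2%). With no events, 0/44 still gives an upper limit of 8.0%.

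**The case against.** The case on the other side has several parts, and some of it stands.

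- *The SAP may modify the protocol.* Both documents say so (protocol 9, SAP 2), and only major changes to the primary endpoint or its analysis need an amendment. This stands: a reader might infer a procedural breach, and there is none. But the SAP's summary of changes says only that AESI in 6.6.1.1 was updated. It gives no reason for reducing a secondary safety analysis.
- *VOD is counted elsewhere.* This also stands. Treatment-emergent and post-HSCT VOD appear by preferred term in unconditional tables, so it would be wrong to say that the SAP drops VOD. What those tables lack are CIs, a stated HSCT denominator and the direct-to-HSCT split.
- *The condition hardly bites.* At pivotal rates the chance of no VOD in 44 patients is (1 − 23/164)^44 = 0.1%, and of none among 21 transplanted patients (1 − 18/79)^21 = 0.4%. So the data would almost surely permit the summary. That is equally a reason to drop the condition.
- *The direct row nearly repeats the all-HSCT row, and anyone can compute a CI.* At pivotal rates it covers 19 of 21 patients, so little information is lost. It is still a promised output that nothing in the SAP produces.
- *The 2-year sentence is the exception to the window.* This is the more natural reading. The sentence directly precedes the VOD count in 6.6.1.1, and a row for VOD after post-study HSCT presupposes later data. A reader might infer that the SAP will certainly leave post-HSCT VOD out of its summaries; the text does not support that. The uncertainty is confined to the overall count and the AESI table.
- *Conditioning may be settled by the eCRF.* SAP 5.2.5 uses any start date on the follow-up cancer therapy pages. If conditioning is entered there, the window closes and the 4/44 reading falls away. Protocol Table 1 footnote 19 groups conditioning with new anti-leukemic therapy, which makes this likely. SAP 5.2.5 does not say so.

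**Conclusion.** The point holds as a shortfall between protocol 9.4.2 and SAP 6.6.1.1: no CIs, no direct-to-HSCT rate, no labelled on-treatment row, and a condition that the protocol does not have. This rests on the text alone and I hold it with high confidence. It should be fixed, but the primary endpoint and data collection are unaffected.

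The window is a secondary point about clarity. The 2-year sentence is probably meant as the exception, but it is worded as a reporting rule. The spread of about 6, 4 or 1 case in 44 shows what hangs on stating it. It is not a forecast. It assumes pivotal VOD and HSCT rates, and the middle figure also rests on assumed log-normal spreads, independence, and average VOD risk in transplants that were not direct.

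**What to change.** 1. In SAP 3.5, 3.5.1 and 6.6.1.1, state that VOD/SOS is summarized from first dose to 2 years or data cutoff, regardless of new anti-cancer therapy.
2. Delete the data-permitting condition in 6.6.1.1.
3. Report total VOD; on-treatment VOD (SAP 3.5 window, before any HSCT); post-HSCT VOD in all transplanted patients and in those transplanted without intervening induction; and a remaining row for VOD with no preceding HSCT after the window. The on-treatment, all-transplanted and remaining counts then sum to the total, with each patient classed by first onset. Give each row its denominator and a two-sided 95% Clopper-Pearson CI.
4. In 5.2.5, say whether HSCT conditioning counts as new anti-cancer therapy.
5. Footnote the AESI and Serious TEAE tables on whether post-HSCT VOD is included.

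If the sponsor prefers to omit the direct-to-HSCT row, the SAP should record why.

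**Cost.** SAP wording, one more table and two footnotes. No new data: VOD is already collected to 2 years, and 5.2.5 already derives the start of new induction therapy, which identifies direct transplants. The CIs will be wide and the reported VOD rates may be higher.
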